### **Aims and hypotheses**

**Primary Aim 1:** To examine whether measuring unattended clinic BP with an automated device will provide a more accurate estimate of awake BP on ABPM than measuring attended clinic BP with an automated device.

**Hypothesis 1a:** The absolute difference with awake BP will be smaller for unattended vs. attended clinic BP.

**Hypothesis 1b:** The agreement between hypertension status using BP measured in the clinic and on ABPM while awake will be higher when clinic BP is measured unattended vs. attended. Also, the prevalence of both white coat and masked hypertension will be lower when measuring unattended clinic BP.

**Primary Aim 2:** To examine whether a new HBPM device provides an accurate approach for measuring sleep BP.

**Hypothesis 2a:** Sleep BP on HBPM will provide an accurate estimate of sleep BP on ABPM.

**Hypothesis 2b:** HBPM will be better tolerated (e.g., less awakening during sleep, pain, bruising) than ABPM.

**Primary Aim 3:** To compare the associations of unattended versus attending clinic BP, unattended clinic BP versus awake BP on ABPM, and sleep BP on HBPM versus ABPM with two markers of end-organ damage, left ventricular mass index (LVMI) and urinary albumin-to-creatinine ratio (ACR).

**Hypothesis 3a:** The association with end-organ damage will be stronger for unattended vs. attended clinic BP.

**Hypothesis 3b:** The association with end-organ damage will be similar for unattended clinic BP and awake BP.

**Hypothesis 3c:** The association with end-organ damage will be similar for sleep BP by HBPM and ABPM.

### **Objectives:**

1. Determine the absolute mean difference in awake systolic and diastolic BP, separately, between attended and unattended BP; awake BP from ABPM and attended BP; and awake BP from ABPM and unattended BP.
2. Determine the prevalence of hypertension, white coat hypertension, and masked hypertension on attended, unattended, and ABPM BP measurements.
3. Determine the agreement between hypertension phenotypes on ABPM and clinic BP (i.e., attended and unattended).
4. Determine the absolute mean difference in asleep systolic and diastolic BP, separately, between asleep BP measurements from ABPM and HBPM.
5. Determine the tolerability of ABPM and HBPM.

6. Determine the associations of unattended versus attending clinic BP, unattended clinic BP versus awake BP on ABPM, and sleep BP on HBPM versus ABPM with left ventricular mass index (LVMi) and urinary albumin-to-creatinine ratio (ACR).

The following will be conducted using data from the Better BP study.

#### **Data management:**

Create the following variables to define hypertension:

1. Create the variable ABPM\_HYPER by assigning 1 to those with mean awake ABPM  $\geq 135$  mm Hg (systolic BP) or 85 mm Hg (diastolic BP) and 0 if otherwise.
2. Create the variable ATTENDED\_HYPER by assigning 1 to those with mean attended BP  $\geq 140$  mm Hg (systolic BP) or 90 mm Hg (diastolic BP) and 0 if otherwise.
3. Create the variable UNATTENDED\_HYPER by assigning 1 to those with mean unattended BP  $\geq 135$  mm Hg (systolic BP) or 85 mm Hg (diastolic BP) and 0 if otherwise.
4. Identify the following individuals:
  1. HYP\_AB\_ATTEND should equal 1 if ABPM\_HYPER = 1 and ATTENDED\_HYPER = 1, and 0 if otherwise.
  2. HYP\_AB\_UNATTEND should equal 1 if ABPM\_HYPER = 1 and UNATTENDED\_HYPER = 1, and 0 if otherwise.
  3. WHIT\_AB\_ATTEND should equal 1 if ABPM\_HYPER = 0 and ATTENDED\_HYPER = 1, and 0 if otherwise.
  4. WHIT\_AB\_UNATTEND should equal 1 if ABPM\_HYPER = 0 and UNATTENDED\_HYPER = 1, and 0 if otherwise.
  5. MASK\_AB\_ATTEND should equal 1 if ABPM\_HYPER = 1 and ATTENDED\_HYPER = 0, and 0 if otherwise.
  6. MASK\_AB\_UNATTEND should equal 1 if ABPM\_HYPER = 1 and UNATTENDED\_HYPER = 0, and 0 if otherwise.

#### **Statistical analysis:**

1. Calculate the distribution of the variables in **Table 1**, overall, and separately for participants who were attended then unattended, unattended then attended, as well as participants who underwent ABPM before HBPM, and HBPM before ABPM.
2. Do the following analysis for **Table 2** for those with complete BP data on ABPM, attended, and unattended:
  - a. For awake systolic BP, calculate the mean (with standard deviation) BP on ABPM, attended, and unattended
  - b. Calculate the absolute mean difference with 95% confidence intervals for ABPM vs. attended, ABPM vs. unattended, and attended vs. unattended, using mixed model to determine the difference between the differences.
  - c. Repeat items **2a** and **2b** for awake diastolic BP on ABPM, attended and unattended.

3. Do the following analysis for **Table 3** for those with complete BP data on ABPM, attended, and unattended:
  - a. Calculate the percentage (with 95% confidence interval) of participants with hypertension on awake ABPM (i.e., ABPM\_HYPER = 1)
  - b. Calculate the percentage (with 95% confidence interval) of participants with hypertension on attended BP measurements (i.e., ATTENDED\_HYPER = 1).
  - c. Calculate the percentage (with 95% confidence interval) of participants with hypertension on unattended BP measurements (i.e., UNATTENDED\_HYPER = 1).
  - d. Calculate the percentage (with 95% confidence intervals) of participants with hypertension on attended and awake ABPM (i.e., HYP\_AB\_ATTEND = 1).
  - e. Calculate the percentage (with 95% confidence intervals) of participants with hypertension on unattended and awake ABPM (i.e., HYP\_AB\_UNATTEND = 1).
  - f. Calculate the percentage (with 95% confidence intervals) of participants with white coat hypertension on ABPM and attended BP (i.e., WHIT\_AB\_ATTEND = 1).
  - g. Calculate the percentage (with 95% confidence intervals) of participants with white coat hypertension on ABPM and unattended BP (i.e., WHIT\_AB\_UNATTEND = 1)
  - h. Calculate the percentage (with 95% confidence intervals) of participants with masked hypertension on ABPM and attended BP (i.e., MASK\_AB\_ATTEND = 1).
  - i. Calculate the percentage (with 95% confidence intervals) of participants with masked hypertension on ABPM and unattended BP (i.e., MASK\_AB\_UNATTEND = 1)
4. Do the following analysis for those with complete BP data on ABPM, attended, and unattended:
  - a. **Table 4**, use a 2 x 2 table to determine the agreement hypertension on ABPM and clinic BP (i.e., HYP\_AB\_ATTEND versus HYP\_AB\_UNATTEND); provide the p-value from kappa statistics.
  - b. **Table 5**, use a 2 x 2 table to determine the agreement white coat hypertension on ABPM and clinic BP (i.e., WHIT\_AB\_ATTEND versus WHIT\_AB\_UNATTEND); provide the p-value from kappa statistics.
  - c. **Table 6**, use a 2 x 2 table to determine the agreement masked hypertension on ABPM and clinic BP (i.e., WHIT\_AB\_ATTEND versus WHIT\_AB\_UNATTEND); provide the p-value from kappa statistics.
5. Do the following analysis for **Table 7** for those with complete sleep BP data on ABPM and HBPM:
  - a. For sleep systolic BP, calculate the mean BP (with standard deviation) on ABPM and HBPM.
  - b. Calculate the absolute mean difference with 95% confidence intervals for ABPM vs. HBPM, using a paired T-test.
  - c. Repeat items 5a and 5b for sleep diastolic BP on ABPM and HBPM.
6. **Table 8**. Calculate the number and percentage of side effects and tolerability (**listed in Table 8**) that occurred in ABPM only, HBPM only, both ABPM and HBPM, and occurred for neither ABPM nor HBPM.
7. **Table 9**. Restrict the analysis to those with complete data on attended and unattended BP and complete data on left ventricular mass index .
  - a. Use linear regression to determine the relationship between attended SBP with left ventricular mass index.
  - b. Repeat the analysis for attended DBP, unattended SBP, unattended DBP with left ventricular mass index, separately.

8. **Table 10.** Restrict the analysis to those with complete BP data on unattended and awake ABPM and complete data on left ventricular mass index.
  - a. Use linear regression to determine the relationship between unattended SBP with left ventricular mass index.
  - b. Repeat the analysis for unattended DBP, awake SBP on ABPM, awake DBP on ABPM with left ventricular mass index, separately.
9. **Table 11.** Restrict the analysis to those with complete sleep BP data on ABPM and HBPM and complete data on left ventricular mass index.
  - c. Use linear regression to determine the relationship between sleep SBP on ABPM with left ventricular mass index.
  - d. Repeat the analysis for sleep DBP on ABPM, sleep SBP on HBPM, and sleep DBP on HBPM with left ventricular mass index, separately.
10. **Table 12.** Restrict the analysis to those with complete data on attended and unattended BP and complete data on urinary albumin-to-creatinine ratio.
  - c. Use linear regression to determine the relationship between attended SBP with urinary albumin-to-creatinine ratio.
  - d. Repeat the analysis for attended DBP, unattended SBP, unattended DBP with urinary albumin-to-creatinine ratio, separately.
11. **Table 13.** Restrict the analysis to those with complete BP data on unattended and awake ABPM and complete data on urinary albumin-to-creatinine ratio.
  - e. Use linear regression to determine the relationship between unattended SBP with urinary albumin-to-creatinine ratio.
  - f. Repeat the analysis for unattended DBP, awake SBP on ABPM, awake DBP on ABPM with urinary albumin-to-creatinine ratio, separately.
12. **Table 14.** Restrict the analysis to those with complete sleep BP data on ABPM and HBPM and complete data on urinary albumin-to-creatinine ratio.
  - g. Use linear regression to determine the relationship between sleep SBP on ABPM with urinary albumin-to-creatinine ratio.
  - h. Repeat the analysis for sleep DBP on ABPM, sleep SBP on HBPM, and sleep DBP on HBPM with urinary albumin-to-creatinine ratio, separately.

Table 1. Characteristics of Better BP participants by randomization.

	Overall N = 603	Attended then unattended, N = 301	Unattended then attended, N = 302	ABPM then HBPM, N = 302	HBPM then ABPM, N = 301
Age, yrs,					
Mean (SD)	38.6 (15.1)	39.4 (16.0)	37.9 (14.1)	39.2 (15.7)	38.1 (14.5)
Median (min – max)	34.0 (18.0 - 83.0)	35.0 (19.0 - 83.0)	34.0 (18.0 - 83.0)	35.5 (18.0 - 79.0)	33.0 (19.0 - 83.0)
Women, %	382 (63.3)	190 (63.1)	192 (63.6)	191 (63.2)	191 (63.5)
Race, %					
Hispanic	39 (6.5)	24 (8.0)	15 (5.0)	22 (7.3)	17 (5.6)
Non-Hispanic, Asian	90 (14.9)	39 (13.0)	51 (16.9)	47 (15.6)	43 (14.3)
Non-Hispanic, Black	132 (21.9)	64 (21.3)	68 (22.5)	61 (20.2)	71 (23.6)
Non-Hispanic, White	291 (48.3)	150 (49.8)	141 (46.7)	148 (49.0)	143 (47.5)
Other non-Hispanic race/ethnicity	51 (8.5)	24 (8.0)	27 (8.9)	24 (7.9)	27 (9.0)
Body Mass Index					
Mean (SD)	27.2 (5.9)	26.8 (5.9)	27.5 (5.8)	27.2 (5.6)	27.2 (6.1)
Median (min – max)	25.9 (13.0 - 55.5)	25.6 (13.0 - 55.5)	26.5 (17.2 - 53.0)	26.0 (13.0 - 53.0)	25.9 (17.3 - 55.5)
Attended office blood pressure					
Systolic BP					
Mean (SD)	119.4 (12.0)	118.9 (12.1)	120.0 (12.0)	119.7 (11.9)	119.2 (12.2)
Median (min – max)	118.2 (92.2 - 179.5)	117.5 (92.2 - 179.5)	118.7 (95.2 - 170.7)	118.3 (94.2 - 161.2)	117.8 (92.2 - 179.5)
Diastolic BP					
Mean (SD)	72.7 (7.8)	72.5 (7.9)	72.9 (7.8)	72.7 (7.5)	72.7 (8.1)
Median (min – max)	71.5 (53.5 - 97.7)	71.0 (53.5 - 97.7)	71.7 (54.8 - 96.3)	71.6 (53.5 - 95.5)	71.3 (59.2 - 97.7)
Unattended office blood pressure					
Systolic BP					
Mean (SD)	118.7 (11.8)	118.2 (11.8)	119.2 (11.8)	119.0 (11.6)	118.3 (12.1)
Median (min – max)	117.3 (90.5 - 179.8)	116.8 (90.5 - 179.8)	117.8 (95.2 - 179.0)	117.7 (91.7 - 158.5)	116.8 (90.5 - 179.8)
Diastolic BP					
Mean (SD)	72.2 (7.7)	71.8 (7.8)	72.5 (7.6)	72.1 (7.5)	72.2 (7.9)
Median (min – max)	71.0 (47.2 - 98.5)	70.8 (47.2 - 98.5)	71.4 (55.7 - 96.8)	71.3 (47.2 - 94.5)	70.8 (57.8 - 98.5)

Table 1 continued.

Ambulatory blood pressure monitoring					
Awake systolic BP					
Mean (SD)	118.7 (10.2)	118.4 (10.4)	119.1 (9.9)	119.2 (10.0)	118.3 (10.4)
Median (min – max)	117.8 (87.6 - 172.8)	117.3 (87.6 - 172.8)	118.3 (97.5 - 154.5)	118.3 (96.7 - 154.5)	117.5 (87.6 - 172.8)
Awake diastolic BP					
Mean (SD)	74.2 (7.0)	73.8 (7.0)	74.6 (7.0)	74.4 (6.8)	74.0 (7.2)
Median (min – max)	73.3 (52.9 - 98.9)	73.1 (52.9 - 94.0)	73.7 (60.3 - 98.9)	73.5 (60.3 - 91.3)	73.1 (52.9 - 98.9)
Asleep systolic BP					
Mean (SD)	104.1 (10.5)	104.0 (10.5)	104.1 (10.5)	104.7 (10.6)	103.4 (10.3)
Median (min – max)	103.2 (72.3 - 145.0)	103.0 (77.1 - 145.0)	103.3 (72.3 - 139.4)	103.6 (78.6 - 145.0)	102.8 (72.3 - 136.1)
Asleep diastolic BP					
Mean (SD)	60.3 (7.5)	60.3 (7.7)	60.3 (7.4)	60.4 (7.4)	60.1 (7.6)
Median (min – max)	59.7 (42.1 - 95.4)	59.6 (43.2 - 95.4)	60.2 (42.1 - 89.3)	59.7 (45.1 - 95.4)	59.9 (42.1 - 89.3)
Home blood pressure monitoring					
Asleep systolic BP					
Mean (SD)	106.3 (11.6)	106.5 (11.3)	106.2 (12.0)	105.7 (11.7)	106.9 (11.6)
Median (min – max)	106.0 (74.0 - 159.0)	107.0 (74.0 - 155.0)	105.0 (81.0 - 159.0)	106.0 (80.0 - 159.0)	107.0 (74.0 - 155.0)
Asleep diastolic BP					
Mean (SD)	62.3 (8.3)	62.5 (8.1)	62.1 (8.5)	61.8 (8.3)	62.9 (8.3)
Median (min – max)	62.0 (38.0 - 88.0)	62.0 (42.0 - 85.0)	62.0 (38.0 - 88.0)	61.0 (38.0 - 88.0)	62.0 (44.0 - 86.0)
Hypertension, %	40 (6.6)	25 (8.3)	15 (5.0)	17 (5.6)	23 (7.6)
High cholesterol, %	56 (9.3)	28 (9.3)	28 (9.3)	29 (9.6)	27 (9.0)
Diabetes, %	10 (1.7)	2 (0.7)	8 (2.6)	5 (1.7)	5 (1.7)
Asthma or hay fever, %	68 (11.3)	32 (10.6)	36 (11.9)	32 (10.6)	36 (12.0)
Married, %	213 (35.3)	105 (34.9)	108 (35.8)	102 (33.8)	111 (36.9)
Not living alone, %	152 (25.2)	77 (25.6)	75 (24.8)	78 (25.8)	74 (24.6)
Smoking status, %					
Never	509 (84.6)	250 (83.1)	259 (86.0)	260 (86.1)	249 (83.0)
Former	79 (13.1)	44 (14.6)	35 (11.6)	35 (11.6)	44 (14.7)
Current	14 (2.3)	7 (2.3)	7 (2.3)	7 (2.3)	7 (2.3)

Table 1 continued.

Current drinker, %	405 (67.2)	202 (67.1)	203 (67.2)	202 (66.9)	203 (67.4)
Good self-reported sleep quality, %	179 (30.1)	87 (29.4)	92 (30.8)	89 (30.0)	90 (30.2)
Self-reported physical activity per week, %	2.8 (2.0)	2.9 (2.1)	2.8 (2.0)	2.8 (2.1)	2.9 (1.9)
Mean (SD)	3.0 (0.0 - 20.0)	3.0 (0.0 - 20.0)	3.0 (0.0 - 10.0)	3.0 (0.0 - 20.0)	3.0 (0.0 - 10.0)
Median (min - max)					

**Table 2.** Mean difference in awake systolic and diastolic BP, separately, with ABPM vs. attended BP, ABPM vs. unattended BP, and Attended vs. Unattended BP, N=569

	ABPM Mean (SD) Median (min – max)	Attended Mean (SD) Median (min – max)	Unattended Mean (SD) Median (min – max)	Mean difference for ABPM vs. Attended BP (95% CI)	Mean difference for ABPM vs. Unattended BP (95% CI)	Mean difference for Attended vs. Unattended BP (95% CI)	P (difference in differences = 0)
Awake systolic BP	118.7 (10.2) 117.8 (87.6 - 172.8)	119.4 (12.1) 117.8 (92.2 - 179.5)	118.7 (11.9) 117.2 (90.5 - 179.8)	-0.69 (-1.36, -0.03)	-0.004 (-0.64, 0.64)	0.69 (0.39, 0.99)	<.0001
Awake diastolic BP	74.2 (7.0) 73.3 (52.9 - 98.9)	72.7 (7.8) 71.3 (53.5 - 97.7)	72.2 (7.7) 71.0 (47.2 - 98.5)	1.55 (1.08, 2.03)	2.03 (1.55, 2.51)	0.47 (0.25, 0.69)	<.0001

**Table 3.** The prevalence of hypertension by awake ABPM, attended, and unattended BP reading, N=569

Hypertension	Prevalence (95% CI)
ABPM hypertensive range	10.0 (7.7,12.8)
Attended clinic BP in hypertensive range	7.2 (5.2,9.7)
Unattended clinic BP in hypertensive range	14.1(11.3,17.2)
ABPM and attended clinic BP in hypertensive range	4.6 (3.0,6.6)
ABPM and unattended clinic BP in hypertensive range	6.9 (4.9,9.3)
White coat hypertension	
Hypertensive attended clinic BP with normal ABPM	2.6(1.5,4.3)
Hypertensive unattended clinic BP with normal ABPM	7.2 (5.2,9.7)
Masked hypertension	
Hypertensive ABPM with normal attended clinic BP	5.5 (3.7,7.6)
Hypertensive ABPM with normal unattended clinic BP	3.2 (1.9,5.0)

Hypertension will be defined as:

Awake ABPM readings  $\geq$ 135 or 85 mm Hg

Attended: SBP/DBP readings  $\geq$ 140 or 90 mm Hg

Unattended: SBP/DBP readings  $\geq$ 135 or 85 mm Hg

**Table 4.** Agreement between hypertension on ABPM and clinic BP, N=569

		ABPM and unattended clinic BP in hypertensive range		N (%)
		Yes, %	No, %	
ABPM and attended clinic BP in hypertensive range	Yes, %	25 (4.4)	1 (0.2)	26 (4.6)
	No, %	14 (2.5)	529 (93.0)	543 (95.4)
	N (%)	39 (6.9)	530 (93.2)	569 (100)
Kappa: 0.76				

**Table 5.** Agreement between white coat hypertension on ABPM and clinic BP, N

		Hypertensive unattended clinic BP with normal ABPM		
		Yes, %	No, %	N (%)
Hypertensive attended clinic BP with normal ABPM	Yes, %	15 (2.6)	0 (0.0)	15 (2.6)
	No, %	26 (4.6)	528 (92.8)	554 (97.4)
N (%)		41(7.2)	528 (92.8)	569 (100)

Kappa: 0.52

**Table 6.** Agreement between masked hypertension on ABPM and clinic BP, N

		Hypertensive ABPM with normal unattended clinic BP		
		Yes, %	No, %	N (%)
Hypertensive ABPM with normal attended clinic BP	Yes, %	17 (3.0)	14 (2.5)	31 (5.5)
	No, %	1 (0.2)	537 (94.4)	538 (94.6)
N (%)		18 (3.2)	551 (96.8)	569 (100)
Kappa: 0.68				

**Table 7.** The difference between sleep BP on HBPM versus sleep BP on ABPM, N = 547

	ABPM Mean (SD) Median, (min – max)	HBPM Mean (SD) Median (min – max)	Mean difference, (95% CI)	P (difference = 0)
Sleep systolic BP	104.1 (10.5) 103.3 (72.3 - 145.0)	106.4 (11.5) 106.0 (74.0 - 159.0)	-2.3 (-3.0, -1.5)	<.0001
Sleep diastolic BP	60.4 (7.5) 59.8 (42.1 - 95.4)	62.3 (8.3) 62.0 (38.0 - 88.0)	-1.9 (-2.5,-1.4)	<.0001

**Table 8.** Side effects and tolerability of HBPM versus ABPM, N = 603.

	Occurred with ABPM only, N (%)	Occurred with HBPM only, N (%)	Occurred with both ABPM and HBPM, N (%)	Didn't occur for ABPM or HBPM, N (%)
Side effects				
Pain while wearing the monitor	160 (26.5)	37 (6.1)	128 (21.2)	278 (46.1)
Irritation while wearing the monitor	178 (29.5)	26 (4.3)	232 (38.5)	167 (27.7)
Bruising while wearing the monitor	84 (13.9)	19 (3.2)	54 (9.0)	446 (74.0)
Tolerability				
Monitor was heavy to wear	133 (22.1)	57 (9.5)	139 (23.1)	274 (45.4)
Monitor was uncomfortable to wear	109 (18.1)	68 (11.3)	399 (66.2)	27 (4.5)
Monitor was straightforward to use	12 (2.0)	6 (1.0)	578 (95.9)	7 (1.2)
Monitor was cumbersome or awkward to wear	130 (21.6)	27 (4.5)	377 (62.5)	69 (11.4)
Noise of the monitor was disturbing to me	91 (15.1)	71 (11.8)	102 (16.9)	339 (56.2)
Noise of the monitor disturb others	67 (11.1)	24 (4.0)	43 (7.1)	469 (77.8)
Monitor was embarrassing to wear	212 (35.2)	10 (1.7)	93 (15.4)	288 (47.8)
Monitor interfered with normal sleeping pattern	124 (20.6)	56 (9.3)	219 (36.3)	204 (33.8)
Removed monitor due to disturbance while sleeping	23 (3.8)	23 (3.8)	16 (2.7)	541 (89.7)

**Table 9.** The relationship between attended and unattended clinic BP with left ventricular mass index (g/m^2), N=587.

Model	Unstandardized beta	Lower limit of 95% confidence intervals for beta	Upper limit of 95% confidence intervals for beta	Standard Error	t-statistic	P-value	Standardized beta
Attended clinic systolic BP	0.43	0.32	0.55	0.06	7.55	<.001	0.30
Attended clinic diastolic BP	0.42	0.24	0.60	0.09	4.66	<.001	0.19
Unattended clinic systolic BP	0.44	0.33	0.56	0.06	7.50	<.001	0.30
Unattended clinic diastolic BP	0.37	0.19	0.55	0.09	4.04	<.001	0.16

Dependent variable: left ventricular mass index (g/m^2) as continuous variable

**Table 10.** The relationship between unattended clinic BP versus awake BP on ABPM with left ventricular mass index (g/m^2), N=554

Model	Unstandardized beta	Lower limit of 95% confidence intervals for beta	Upper limit of 95% confidence intervals for beta	Standard Error	t-statistic	P-value	Standardized beta
Unattended systolic BP	0.44	0.32	0.56	0.06	7.38	<0.001	0.30
Unattended diastolic BP	0.38	0.19	0.56	0.09	3.99	<0.001	0.17
Awake systolic BP on ABPM	0.61	0.47	0.74	0.07	8.69	<0.001	0.35
Awake diastolic BP on ABPM	0.45	0.25	0.66	0.10	4.36	<0.001	0.18

Dependent variable: left ventricular mass index (g/m^2) as continuous variable

**Table 11.** The relationship between sleep BP on H BPM versus ABPM with left ventricular mass index (g/m^2), N=533

Model	Unstandardized beta	Lower limit of 95% confidence intervals for beta	Upper limit of 95% confidence intervals for beta	Standard Error	t-statistic	P-value	Standardized beta
Sleep systolic BP on H BPM	0.31	0.19	0.44	0.06	4.98	<0.001	0.21
Sleep diastolic BP on H BPM	0.23	0.05	0.40	0.09	2.54	0.01	0.11
Sleep systolic BP on ABPM	0.45	0.32	0.59	0.07	6.63	<0.001	0.28
Sleep diastolic BP on ABPM	0.36	0.16	0.55	0.10	3.64	<0.001	0.16

Dependent variable: left ventricular mass index (g/m^2) as continuous variable

**Table 12.** The relationship between attended and unattended clinic BP with urinary albumin-to-creatinine ratio (mg/g), N=555.

Model	Unstandardized beta	Lower limit of 95% confidence intervals for beta	Upper limit of 95% confidence intervals for beta	Standard Error	t-statistic	P-value	Standardized beta
Attended clinic systolic BP	-0.2	-0.47	0.08	0.14	-1.39	0.17	-0.06
Attended clinic diastolic BP	-0.28	-0.7	0.15	0.22	-1.27	0.20	-0.05
Unattended clinic systolic BP	-0.26	-0.55	0.02	0.14	-1.84	0.07	-0.08
Unattended clinic diastolic BP	-0.37	-0.8	0.06	0.22	-1.68	0.09	-0.07

Dependent variable: urinary albumin-to-creatinine ratio (mg/g) as continuous variable

**Table 13.** The relationship between unattended clinic BP versus awake BP on ABPM with urinary albumin-to-creatinine ratio (mg/g), N=523.

Model	Unstandardized beta	Lower limit of 95% confidence intervals for beta	Upper limit of 95% confidence intervals for beta	Standard Error	t-statistic	P-value	Standardized beta
Unattended systolic BP	-0.18	-0.44	0.07	0.13	-1.39	0.16	-0.06
Unattended diastolic BP	-0.09	-0.49	0.31	0.20	-0.45	0.65	-0.02
Awake systolic BP on ABPM	0.01	-0.29	0.31	0.15	0.07	0.94	0.00
Awake diastolic BP on ABPM	0.22	-0.21	0.66	0.22	1.01	0.31	0.04

**Table 14.** The relationship between sleep BP on H BPM versus ABPM with urinary albumin-to-creatinine ratio (mg/g), N=505.

Model	Unstandardized beta	Lower limit of 95% confidence intervals for beta	Upper limit of 95% confidence intervals for beta	Standard Error	t-statistic	P-value	Standardized beta
Sleep systolic BP on H BPM	-0.01	-0.28	0.26	0.14	-0.08	0.94	-0.00
Sleep diastolic BP on H BPM	-0.02	-0.40	0.36	0.20	-0.09	0.93	-0.00
Sleep systolic BP on ABPM	0.09	-0.21	0.40	0.15	0.61	0.54	0.03
Sleep diastolic BP on ABPM	0.26	-0.16	0.68	0.21	1.20	0.23	0.05

Dependent variable: urinary albumin-to-creatinine ratio (mg/g) as continuous variable

The standard approach to measuring blood pressure (BP), in the clinic with an observer present (attended BP measurement), results in the misdiagnosis of hypertension for many adults. Among adults with high BP in the clinic (systolic BP [SBP]/diastolic BP [DBP]  $\geq 140/90$  mm Hg), ~20% to 30% do not have high BP (SBP/DBP  $<135/85$  mm Hg) while awake outside of the clinic, a phenotype called white coat hypertension. White coat hypertension is not associated with increased cardiovascular disease (CVD) risk. Also, 15% to 30% of people without high BP (SBP/DBP  $<140/90$  mm Hg) when measured by an observer in the clinic have high BP (SBP/DBP  $\geq 135/85$  mm Hg) while awake outside of the clinic. This phenotype, called masked hypertension, is associated with high CVD risk. Due to the high degree of misclassification of hypertension when using clinic BP, the US Preventive Services Task Force recommends out-of-clinic BP measurement be performed to exclude the presence of white coat hypertension before initiating antihypertensive treatment.

Data from non-randomized studies from Canada suggest that using an automated oscillometric BP (AOBP) device without an observer present (unattended BP) results in lower clinic BP compared to attended measurements taken using the auscultatory method. *The 2017 Canadian hypertension guideline recommended measuring unattended BP in clinical practice for reducing the risk of white coat hypertension but acknowledged the low level of evidence supporting this recommendation (i.e., Grade D, “very low quality” and “expert opinion”). Currently, obtaining unattended BP has not been adopted in US guidelines. Few studies have compared unattended clinic BP to attended clinic BP measured with an oscillometric device, which is increasingly being used for measuring BP in the US. In an analysis of the Systolic Blood Pressure Intervention Trial (SPRINT) data, there was no difference in BP when measured unattended and attended (personal communication, [name]). Thus, there is equipoise as to whether unattended BP reduces the risk of white coat hypertension. Further, the effect of unattended BP measurement on masked hypertension risk is also unclear.*

Nocturnal hypertension, typically defined by mean sleep SBP/DBP  $\geq 120/70$  mm Hg, affects ~1 in 3 adults and is associated with increased CVD risk, independent of clinic and awake BP. Therefore, a comprehensive approach to diagnosing hypertension requires measuring sleep BP in addition to awake BP. Ambulatory BP monitoring (ABPM) is a procedure wherein people have their BP measured automatically every 15 to 30 minutes, typically for 24 hours, outside of the clinic setting. ABPM is widely considered to be the reference standard for diagnosing hypertension. However, ABPM is not available in most clinics in the US and is poorly tolerated by patients. Recently, home BP monitoring (HBPM) devices have been developed that measure BP during sleep. These devices may be better tolerated than ABPM as they are only worn at night and fewer BP measurements are obtained. **We propose to compare novel non-ABPM approaches for measuring BP and diagnosing hypertension with ABPM, the reference standard.** The study aims are:

**Aim 1. Test whether measuring unattended clinic BP with an automated device will provide a more accurate estimate of awake BP on ABPM than measuring attended clinic BP with an automated device.**

*Hypothesis 1a: The absolute difference with awake BP will be smaller for unattended vs. attended clinic BP.*

*Hypothesis 1b: The agreement between hypertension status using BP measured in the clinic and on ABPM while awake will be higher when clinic BP is measured unattended versus attended. Also, the prevalence of both white coat and masked hypertension will be lower when measuring unattended versus attended clinic BP.*

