**D.11.3. Exploratory statistics comparing unattended and attended BP.** We will calculate characteristics of participants by randomization assignment: unattended then attended clinic BP measurement or attended then unattended clinic BP measurement at the first visit. Scatterplots will be assembled to show the relationship between unattended clinic BP versus awake BP and attended clinic BP versus awake BP. For each comparison, intraclass correlation coefficients will be calculated. The statistical significance of the difference in the correlation coefficients will be calculated using the Fisher r-to-z transformation accounting for the correlation between attended and unattended clinic BP. We will also assemble Bland-Altman plots showing the differences between unattended and attended BP, separately, versus awake BP on ABPM.

**D.11.4. Aim 1. Test whether measuring unattended clinic BP with an automated device will provide a more accurate estimate of awake BP on ABPM than measuring attended clinic BP with an automated device.** Our primary analyses for Hypothesis 1 will be tested using the first three clinic BP measurements obtained at Visits 1 and 2. In sensitivity analyses, we will use the fourth through sixth BP measurements from these visits. Separate analyses will be performed for SBP and DBP.

**D.11.4.1. Hypothesis 1a: The absolute difference with awake BP will be smaller for unattended vs. attended clinic BP.** The absolute difference between mean unattended clinic BP and awake BP and mean attended clinic BP and awake BP, separately, will be calculated. We will test whether these differences are statistically significantly different from zero using paired t-tests. Next, we will determine whether the absolute difference between unattended clinic BP and awake BP is smaller than the absolute difference between attended clinic BP and awake BP by calculating if the difference in differences (i.e., absolute difference between unattended clinic BP and awake BP minus the absolute difference between attended clinic BP and awake BP) is less than zero using a paired t-test. If the absolute differences between unattended and attended clinic BP and awake BP differs by randomization assignment, we will use a mixed model with randomization assignment as a covariate. This analysis will be performed in the overall population and in sub-groups defined by age (categorized in tertiles), race/ethnicity (white, African American, Hispanic) and sex.

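### Analysis Plan item 2b and Table 2 give no test of Hypothesis 1a: with signed differences awake ABPM cancels, and the printed P-value appears to be attended versus unattended

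*Combined protocol and SAP*

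**What the plan says.** **Hypothesis.** The Analysis Plan (Aims and hypotheses) states Hypothesis 1a as "The absolute difference with awake BP will be smaller for unattended vs. attended clinic BP".

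**Protocol test.** D.11.4.1 forms the absolute difference for unattended "minus the absolute difference between attended clinic BP and awake BP) is less than zero using a paired t-test". If the differences vary by randomised order, it moves to a mixed model with order as a covariate. The same section also says "We will test whether these differences are statistically significantly different from zero using paired t-tests". That step suits signed differences only, because a mean of absolute values is positive whenever readings differ at all.

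**Analysis Plan.** Objective 1 and item 2b speak of an absolute mean difference. Item 2b then names the pairwise comparisons, ending "and attended vs. unattended, using mixed model to determine the difference between the differences". It does not say that an absolute value is taken per participant, which direction supports the hypothesis, or what terms the mixed model contains.

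**Table 2 (N=569).** The two differences from ABPM carry their signs, and the last column is headed "P (difference in differences = 0"). Both rows read <.0001. Item 5b uses the same phrase for sleep BP ("Calculate the absolute mean difference with 95% confidence intervals for ABPM vs. HBPM, using a paired T-test"), and Table 7 again prints signed values (-2.3 and -1.9).

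**The concern.** Hypothesis 1a is the first hypothesis of Primary Aim 1, and it concerns closeness to a reference standard. A contrast in which the reference cancels cannot show which clinic method is closer to it. The heading of the Table 2 P column echoes the term that D.11.4.1 uses for the Hypothesis 1a test, so readers will take <.0001 as that result.

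The DBP row shows the danger. Its P is as small as the SBP one, yet unattended lies farther from ABPM on average (2.03 against 1.55 mm Hg), opposite to the hypothesis. No other item or table in the Analysis Plan supplies an estimate, confidence interval or test for the participant-level absolute contrast.

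**Working it through.** **Inputs.** Analysis Plan Table 2, N=569, mean difference (95% CI):

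| | ABPM - attended | ABPM - unattended | Attended - unattended | P |
|---|---|---|---|---|
| SBP | -0.69 (-1.36, -0.03) | -0.004 (-0.64, 0.64) | 0.69 (0.39, 0.99) | <.0001 |
| DBP | 1.55 (1.08, 2.03) | 2.03 (1.55, 2.51) | 0.47 (0.25, 0.69) | <.0001 |

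**1. The identity.** For every participant,

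(ABPM - unattended) - (ABPM - attended) = attended - unattended.

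The printed columns close accordingly:
- SBP: -0.004 - (-0.69) = 0.686, printed 0.69.
- DBP: 2.03 - 1.55 = 0.48, printed 0.47.

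**2. Reproducing the printed P.** SE = CI half-width / t(.975, 568), with t = 1.964.
- SBP: SE = 0.30/1.964 = 0.153; t = 0.69/0.153 = 4.52; P = 7.6e-6.
- DBP: SE = 0.22/1.964 = 0.112; t = 0.47/0.112 = 4.20; P = 3.2e-5.

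Both are below .0001, without any ABPM reading.

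**3. The participant-level absolute contrast (illustrative).** SD = SE × √569, and the correlation of the two differences from ABPM follows from r = (s₁² + s₂² - s₃²)/(2s₁s₂).
- SBP: SDs 8.08, 7.77, 3.64; r = 0.895.
- DBP: SDs 5.77, 5.83, 2.67; r = 0.894.

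Assuming bivariate normality, E|D| = s√(2/π)·exp(-m²/2s²) + m[1 - 2Φ(-m/s)]. The SE of the contrast comes from simulation with these SDs and correlations.

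| | Mean absolute difference, attended | Unattended | Unattended - attended | SE | Two-sided P |
|---|---|---|---|---|---|
| SBP | 6.47 | 6.20 | -0.27 | 0.14 | about 0.06 |
| DBP | 4.77 | 4.93 | +0.16 | 0.10 | about 0.11 |

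**4. Sensitivity to the reference, on the same measure.** Move every awake SBP by a constant and recompute the SBP mean absolute differences:

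| Shift in awake SBP | Attended | Unattended | Closer method | Signed contrast |
|---|---|---|---|---|
| none | 6.47 | 6.20 | unattended | 0.686 |
| +5 mm Hg | 7.34 | 7.44 | attended | 0.686 |
| -5 mm Hg | 7.98 | 7.44 | unattended | 0.686 |

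The closer method changes. The signed contrast, and so its P, does not.

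**5. An alternative source of the printed P.** A 2-df Wald test that all three means are equal gives chi-square of about 20.6 for SBP (P about 3e-5) and about 74 for DBP (P far below .0001). This also matches <.0001.

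**The case against.** **The phrase may mean the absolute value of the group mean difference.** This is the strongest reply. Within each row of Table 2 the two mean differences from ABPM share a sign, so that contrast has the same size as attended versus unattended, and the printed P could serve it. It would then compare average bias rather than closeness per participant. It would still be undirected, and for DBP it favours attended. D.11.4.1 points to the participant level, because a paired t-test needs one value per person.

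**The contrast is inferred.** This stands. The mixed model is unspecified and P is printed only as a bound. A reader might infer that the P-value is shown to be independent of ABPM. The documents do not establish that, since the 2-df test uses ABPM and also fits. That test would not address Hypothesis 1a either.

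**The protocol has other accuracy analyses.** D.11.3 plans intraclass correlations with awake BP, a test of their difference, and Bland-Altman plots. These bear on closeness, but they are labelled exploratory and have no table in the Analysis Plan.

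**Readers can see the means.** True: the signed means and intervals are printed, so the DBP direction is visible. An estimate of the contrast that the hypothesis names is not.

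**D.11.4.1 is itself mixed.** Also true. If it were read as signed throughout, the Analysis Plan would follow it and both would miss the hypothesis.

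**Conclusion.** The point holds. Item 2b and Table 2 provide no test of the participient-level contrast behind Hypothesis 1a, and the <.0001 entries in that slot appear to be the attended versus unattended comparison. The absence of the test follows from the text and the algebra. The source of the printed P is probable, pending the code.

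The sizes in step 3 assume bivariate normality and take the rounded Table 2 figures at their central values. A reader might infer from them that the correct P must be unremarkable, or that Hypothesis 1a has failed. Neither is supported: printed means and intervals do not fix the sample mean of an absolute difference, so no lower bound on P can be claimed, and significance at 5% remains open until the raw data are analysed.

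D.11.4 bases its primary analysis on the "first three clinic BP measurements obtained at Visits 1 and 2". Which readings Table 2 uses is a separate question, and the illustration does not estimate the contrast on that set.

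**What to change.** 1. In item 2b and Table 2, compute |unattended - awake ABPM| and |attended - awake ABPM| for each participant.
2. Test the within-person difference (unattended minus attended) with a paired t-test, or with a mixed model including randomised order as D.11.4.1 provides. Report it for SBP and DBP with its direction and a two-sided 95% CI, as the Hypothesis 1a result.
3. Keep the signed mean differences, labelled as estimates of average bias.
4. Check the code. If it confirms the contrast, relabel the present P column as attended versus unattended.
5. In D.11.4.1, limit the tests against zero to signed differences.
6. Record that the change was made after results were seen.

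The cost is revised wording, a few lines of code, a re-run of Table 2 and a deviation note. No new data are needed. The new P-values may look less favourable than those now printed.
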